5.1. Inclusion Criteria

Subjects may be eligible for inclusion in the study if they meet the following criteria:

1. Male or female subjects ≥ 18 years of age
2. Histologically confirmed diagnosis of iNHL. Histologic subtypes include FL Grades 1 to 3a, marginal zone lymphoma (splenic, nodal, or extranodal), or SLL
3. Must have received at least 1 prior systemic regimen for iNHL
4. Must have documented radiologic evidence of disease progression, at least 1 bidimensionally measurable lesion ≥ 1.5 cm (which has not been previously irradiated), according to 2007 revised IWG criteria ([Cheson 2007](#)), and be a candidate for a subsequent line of therapy
5. Must have adequate organ function defined by the following laboratory parameters:
 - a. Absolute neutrophil count (ANC) $\geq 1.0 \times 10^9/L$
 - b. Platelet count $\geq 75 \times 10^9/L$
 - c. Hemoglobin ≥ 8 g/dL
 - d. Estimated creatinine clearance (eCCr) ≥ 60 mL/min, as determined by the Cockcroft-Gault method ([Cockcroft 1976](#))
 - e. Total bilirubin $\leq 1.5 \times$ upper limit of normal (ULN) (exception: subjects with Gilbert's Syndrome may have a bilirubin $> 1.5 \times$ ULN)
 - f. Aspartate transaminase (AST)/serum glutamic-oxaloacetic transaminase (SGOT) and alanine aminotransferase (ALT)/serum pyruvic transaminase (SGPT) $\leq 3.0 \times$ ULN
6. Eastern Cooperative Oncology Group (ECOG) performance status ≤ 2
7. Male and female subjects of reproductive potential (i.e., not surgically sterile or female subjects who are not postmenopausal) must be willing to use highly effective methods of contraception (see Section [10.4](#)) for the duration of the study intervention and for 3 months after the last dose of duvelisib
8. Negative serum human chorionic gonadotropin (hCG) pregnancy test within 7 days before first dose of study intervention if the subject is a woman of childbearing potential (WCBP) (defined in Section [10.4](#))
9. Signed and dated institutional review board (IRB)/independent ethics committee (IEC)-approved informed consent form before any study specific-screening procedures are performed

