#### 4.11.2 Adverse Events

Adverse events will be coded using Medical Dictionary for Regulatory Activities (MedDRA) Version 22 or higher. The severity grade of the AE will be assessed by the Investigator according to the National Cancer Institute Common Terminology Criteria for Adverse Events (NCI-CTCAE, Version 5.0). If an AE is not included in the NCI-CTCAE Version 5.0, the severity grade of the AE will be assessed by the Investigator according to the study protocol.

A treatment-emergent adverse event (TEAE) is defined as any AE that emerges or worsens in the period from the first dose of duvelisib to 30 days after the last dose of duvelisib. The onset date of an AE will be compared to the first dose date and the last dose date plus 30 days (inclusive) to determine whether the AE is treatment-emergent or not. Refer to [Section 4.3.1.2](#) for the algorithm to determine whether an AE is treatment emergent if the onset date of an AE is completely or partially missing.

TEAEs will be summarized for each treatment arm by MedDRA SOC and PT, or PT only, or SOC only. For summary tables by SOC and PT, SOC will be sorted alphabetically, and PT will be sorted by decreasing frequency in Arm 1 within each SOC. For summary tables by PT only, PT will be sorted by decreasing frequency. For selected summaries (indicated in the list below), TEAEs will be summarized by SOC, high-level group term (HLGT) and PT, sorted by most frequently occurring SOC.

If multiple TEAEs of the same PT are reported for a subject, only the maximum grade observed for this PT will be included in summary of TEAEs by grade; the subject will be counted only once in the number of subjects for this PT and only once for the number of subjects for the SOC to which the PT is classified.

An overview TEAE summary table will be provided which will include the number of subjects with AEs in selected categories. In addition, TEAEs will be summarized for the following categories, and will be tabulated by SOC and PT, unless otherwise specified.

- TEAEs (all grades, all causalities)
- Treatment-related TEAEs (all grades)
- TEAEs by maximum grade (all causalities)

- Treatment-related TEAEs by maximum grade
- Grade 3 or higher TEAEs (all causalities)
- Grade 3 or higher treatment-related TEAEs
- Treatment-emergent SAEs (all causalities)
- TEAEs resulting in discontinuation of study drug (all causalities)
- TEAEs resulting in dose hold (all causalities)
- TEAEs resulting in dose reduction (all causalities)

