**6 APPENDIX****Appendix 1: List of Preferred Terms for Adverse Events of Special Interest**

Grouped Term	Preferred Terms
All infections (excluding Pneumonia and COVID-19 infections)	All preferred terms under SOC = 'Infections Infections and infestations' excluding any preferred term containing the word 'pneumonia' and excluding any preferred terms included in the COVID-19 infections Grouped Term.
Diarrhea	Diarrhoea, Diarrhoea hemorrhagic, Defecation urgency
Colitis	Colitis, Colitis erosive, Enterocolitis, Enterocolitis hemorrhagic, Colitis microscopic, Necrotising colitis, Colitis ulcerative
Pneumonia	Pneumonia, any PT containing the word/string "pneumonia" except for "Pneumonia aspiration", Atypical pneumonia, Atypical mycobacterial pneumonia, Bronchopneumonia, Bronchopulmonary aspergillosis
Pneumonitis	Pneumonitis, Interstitial lung disease, lung infiltration, acute interstitial pneumonitis
Transaminase elevation	Alanine aminotransferase increased, Aspartate aminotransferase increased, Transaminases increased, Hypertransaminasaemia, Hepatic enzyme increased, Acute hepatic failure, Drug-induced liver injury, Hepatic failure, Hepatocellular injury, Hepatotoxicity
Cutaneous reactions	Dermatitis, Dermatitis allergic, Dermatitis bullous, Dermatitis exfoliative, Dermatitis psoriasiform, Drug eruption, Drug reaction with eosinophilia and systemic symptoms, Erythema, Erythema multiforme, Generalised erythema, Exfoliative rash, Rash, Rash generalised, Rash erythematous, Rash follicular, Rash macular, Rash maculo-papular, Rash maculovesicular, Rash papular, Rash papulosquamous, Rash pruritic, Rash pustular, Rash vesicular, Toxic skin eruption, Palmar erythema, Palmoplantar keratoderma, Palmar-plantar erythrodysesthesia syndrome, Perivascular dermatitis, Skin reaction, skin toxicity, Stevens-Johnson syndrome, Toxic epidermal necrolysis
Neutropenia	Neutropenia, Neutrophil count decreased
COVID-19 infections	Asymptomatic COVID-19, Congenital COVID-19, Coronavirus infection, Coronavirus test positive, COVID-19 pneumonia, COVID-19 treatment, Multisystem inflammatory syndrome in children, Post-acute COVID-19 syndrome, SARS-CoV-2 RNA decreased, SARS-CoV-2 RNA fluctuation, SARS-CoV-2 RNA increased, SARS-CoV-2 sepsis, SARS-CoV-2 test false negative, SARS-CoV-2 test positive, SARS-CoV-2 viraemia, Suspected COVID-19, Vaccine derived SARS-CoV-2 infection

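### The closed COVID-19 AESI list in SAP Appendix 1 omits the plain term 'COVID-19', so any event coded to it would miss the COVID-19 row and could be counted in the row labelled as excluding COVID-19

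*SAP*

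**What the plan says.** SAP 4.11.2.1 plans three infection rows: all infections other than pneumonia and COVID-19, pneumonia, and COVID-19 infections. It refers to Appendix 1 for the PTs that make up each one. The SAP revision history records that the COVID-19 AESI was added in version 2.1.

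In Appendix 1 the COVID-19 group starts "Asymptomatic COVID-19, Congenital COVID-19, Coronavirus infection, Coronavirus test positive, COVID-19 pneumonia, COVID-19 treatment". It continues with "Multisystem inflammatory syndrome in children", the post-acute syndrome, three SARS-CoV-2 RNA terms and SARS-CoV-2 sepsis, and ends "SARS-CoV-2 test false negative, SARS-CoV-2 test positive, SARS-CoV-2 viraemia, Suspected COVID-19, Vaccine derived SARS-CoV-2 infection". Nothing follows that would extend the list.

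The All-infections row takes every PT in the infections SOC, "excluding any preferred term containing the word 'pneumonia' and excluding any preferred terms included in the COVID-19 infections Grouped Term". The Pneumonia row works differently: besides named terms it admits, with one named exception, any PT in which the string 'pneumonia' occurs.

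**The concern.** The list names several qualified forms of COVID-19 but not COVID-19 itself. It does not read as deliberately narrow. It includes a congenital form and a childhood syndrome, although Protocol 5.1 admits only "Male or female subjects ≥ 18 years of age", and it includes test-result terms, even a false-negative test. No section gives a reason for leaving out the plain term. The Pneumonia row shows that the appendix uses an open string rule elsewhere, so its absence here matters.

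The All-infections row removes COVID-19 events only through this list, so one omission can distort two rows. The COVID-19 count could be too low, and the count labelled as excluding COVID-19 could contain COVID-19. Infections are an identified risk of duvelisib (Protocol 2.3.1), so the separation between these rows should be dependable.

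**Working it through.** The plan states no figure to reproduce. The check is to count the list and then apply the row rules to an event coded 'COVID-19'.

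**Step 1: the list (SAP Appendix 1, COVID-19 row).**
- Terms containing 'COVID-19': asymptomatic, congenital, pneumonia, treatment, post-acute, suspected = 6.
- Terms containing 'SARS-CoV-2': three RNA terms, sepsis, false-negative test, positive test, viraemia, vaccine-derived infection = 8.
- Terms containing neither: two coronavirus terms and the childhood syndrome = 3.
- Total 6 + 8 + 3 = 17. Terms equal to 'COVID-19': 0.

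The list is in alphabetical order. The plain term would stand between 'Coronavirus test positive' and 'COVID-19 pneumonia', and nothing marks a removal there.

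**Step 2: where an event coded 'COVID-19' goes.** The documents do not show the dictionary, so both SOC possibilities are taken.

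| Appendix 1 | SOC of the PT | COVID-19 row | Pneumonia row | All-infections row |
|---|---|---|---|---|
| As written | Infections | No | No | Yes |
| As written | Other | No | No | No |
| Plain term added | Infections | Yes | No | No |
| Plain term added | Other | Yes | No | No |

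As written, the event is never in the COVID-19 row. It falls in the wrong row in one case and in no infection row in the other. Adding the term corrects both cases, because the All-infections rule already removes whatever is on the COVID-19 list.

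**Step 3: size.** Let k be the number of subjects in an arm whose only infection event is coded 'COVID-19', and take the planned 51 per arm as a nominal denominator (the safety set counts dosed subjects). If the PT is in the infections SOC, the COVID-19 row loses k/51 and the All-infections row gains k/51.
- k = 1: 1/51 = 2.0 percentage points.
- k = 3: 3/51 = 5.9 points.
- k = 5: 5/51 = 9.8 points.

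The values of k are assumptions for illustration. The documents give no counts, and k may be 0. A subject who also has a listed COVID-19 term does not change the COVID-19 row. A subject already counted in All infections does not change that row.

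**Step 4: a related gap between two rows.** The Pneumonia list includes "Atypical pneumonia, Atypical mycobacterial pneumonia, Bronchopneumonia, Bronchopulmonary aspergillosis". The last of these lacks the word 'pneumonia', so the All-infections exclusion does not catch it. If it is in the infections SOC, it is counted in both rows.

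**The case against.** The strongest objection is that harm depends on things the documents do not show: that the version used has a PT 'COVID-19', which SOC holds it, and that a subject had such an event. This stands as a limit on the conclusion. A reader might infer that COVID-19 cases will certainly be misclassified, and the documents do not support that. It is no reason to leave the list alone, since adding a term that turns out not to be a PT changes nothing.

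A reader might also infer that the mix of events inside the grouped rows would be hidden. That is not supported either. SAP 4.11.2 tabulates dose holds, reductions, discontinuations and resolution status by SOC and PT. SAP 4.11.2.1 shows individual PTs in the subject-level AESI tables, and its by-subject listing of all adverse events gives PT, duration, action taken and outcome. The event-level AESI summaries are by grouped PT only, but the split can be rebuilt from that listing. What remains is a subtotal that does not match its label.

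Four other extensions fail:
- **Stopped arm.** Using the 15 Stage 1 subjects as the denominator for an arm stopped early would give a larger shift per subject. Enrollment is continuous between stages (SAP 3.1), so a stopped arm may hold more than 15.
- **Dictionary version.** SAP 4.11.2 says "Adverse events will be coded using Medical Dictionary for Regulatory Activities (MedDRA) Version 22 or higher" and SAP 4.3.2 says 24.0. These are compatible, because 24.0 meets the first condition.
- **'Pneumonia aspiration'.** The existing rules settle its place: it is in neither row. Wanting it elsewhere is a preference.
- **'Bronchopneumonia'.** Double counting would need a whole-word reading of the exclusion, which is strained when the Pneumonia row treats word and string alike.

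**Conclusion.** The point holds, as a minor one. The omission and the closed list are facts of Appendix 1. Followed exactly, the rules keep any event coded 'COVID-19' out of the COVID-19 row. If the PT is in the infections SOC, they place it in the row labelled as excluding COVID-19, and both grouped counts then disagree with their labels.

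The consequence rests on three assumptions that the documents cannot confirm: the PT exists in the version used, it is in that SOC, and at least one event was coded to it. If any fails, the mislabelling of the All-infections row does not occur; if the PT is in another SOC, the COVID-19 row is still short. The size is about 2.0 percentage points per affected subject in a nominal arm of 51, and possibly zero in total. Only descriptive AESI summaries are involved. ORR, its confidence interval and the error rates are unaffected.

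**What to change.** Add 'COVID-19' to the COVID-19 infections group in SAP Appendix 1. The All-infections row needs no change for this, because its exclusion refers to that group. Before database lock, compare the list once with the terms actually coded, to confirm that no COVID-19 term is left out.

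Optionally, also exclude from All infections every term listed under Pneumonia, so that 'Bronchopulmonary aspergillosis' cannot count in both rows. Keep the present exclusion of terms containing 'pneumonia' alongside it, so that 'Pneumonia aspiration' is not moved into All infections as a side effect.

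The cost is one or two wording edits to one appendix and one check of coded terms. No new data are needed and no efficacy analysis changes.
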